Appendix 2: Schedule of Activities for Cohorts B–D

- Nasopharyngeal swab samples should be collected at screening and once per day on Days 1, 3, 5, and 7. Swab samples should be collected from both nostrils at all timepoints. Screening samples will be used for point-of-care RT-PCR or rapid antigen testing to determine eligibility.
- Sample must be collected prior to dosing.
- Samples for PBMC may not be collected at some timepoints if sample stability requirements for processing will not be met. Please refer to the laboratory manual for more detail. A plasma sample will be generated from the blood sample obtained following PBMC processing and will be stored for biomarker research. No additional blood draw is needed.
- Collection of blood sample for RNA analysis using PAXgene tubes.
- Not applicable for a site that has not been granted approval for WGS. If the sample is not collected on Day 1 for any reason, it may be collected at any later timepoint.
- Randomization will be performed as soon as possible after screening and within 72 hours.
- First dose on Day 1 must be administered as soon as possible after randomization and within 24 hours. For BID regimens, AT-527 (or placebo), should be taken approximately 12 hours apart. If the first dose is taken after 4 pm (16:00 hours) on Day 1, the next dose will be taken in the morning of Day 2. For these patients, the 10th dose will be taken on the morning of Day 6. If the first dose is taken prior to 4 pm (16:00 hours) on Day 1, the next dose should be taken in the evening of the same day (i.e., prior to midnight on the same calendar day with a minimum of 8 hours between doses). For these patients, the 10th dose will be taken in the evening of Day 5. For other dose regimens see Pharmacy manual for details of dosing instruction.
- Medication (e.g., prescription drugs, over-the-counter drugs, vaccines, herbal or homeopathic remedies, nutritional supplements) used by a patient in addition to protocol-mandated treatment from 7 days (12 months for COVID-19 vaccines) prior to initiation of study drug until the end of study follow-up telephone call on Day 33.
- After informed consent has been obtained but prior to initiation of study drug, only serious adverse events caused by a protocol-mandated intervention should be reported. After initiation of study drug, all adverse events will be reported until the end of study follow-up telephone call on Day 33.

Appendix 3
Schedule of Activities for Cohorts E

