Appendix 3: Schedule of Activities for Cohort E

- ^a Screening assessments may be performed up to 72 hours prior to Day 1 or on Day 1.
- ^b An unscheduled visit represents a visit that is not specified by the protocol but is determined to be necessary by the investigator or Sponsor (e.g., for evaluation of an adverse event). Assessments (including PK sample collection) should be performed as clinically indicated. For unscheduled visits occurring after Day 7, PK sample collection is not required.
- ^c Patients who discontinue study drug prematurely will continue to complete assessments as indicated until the end of the study. Patients who discontinue from study participation will have an early termination visit 7 (\pm 2) days after their final dose of study drug. Patients who discontinue from the study after Day 14 will not be required to complete an early termination visit.
- ^d Required follow-up information will be collected at Day 14 (\pm 2 days), and Day 33 (\pm 3 days). Patients in Cohort E are required to have an in-person visit for nasopharyngeal swab collection.
- ^e Informed consent must be documented before any study-specific screening procedure is performed.
- ^f For patients at participating sites who have provided written or electronic informed consent to participate in mobile nursing visits, this assessment or procedure may be performed by a trained nursing professional at the patient's home.
- ^g COVID-19 Symptom Diary includes questions regarding symptoms (Items 1–14) and the Patient Global Impression of Severity. Questionnaires will be self-administered before the patient receives any information on disease status, prior to the performance of non-PRO assessments, and prior to the administration of study treatment. On Day 1, the first diary questionnaire should be completed prior to the first dose. On Days 1–14, the questionnaire (including recording of temperature) should be administered twice a day (morning and evening) at the same time each day.
- ^h On Days 15–28, the questionnaire (including recording of temperature) should be completed once a day in the evening at the same time each day.
- ⁱ Includes oxygen saturation (pulse oximetry), respiratory rate, pulse rate, and systolic and diastolic blood pressure while the patient is in a supine or seated position, and temperature.

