5. STATISTICAL ANALYSES

5.1 GENERAL CONSIDERATION

All virology and efficacy analyses will be performed on the mITTi population.

All primary and secondary virology endpoints will be produced using the nasopharyngeal swab samples. Additional descriptive analyses for saliva and serum samples will be performed on an exploratory basis for the primary and secondary virology endpoints, as required. A summary of the sampling differences between cohorts is provided in [Table 3](#). Refer to Appendix 1 and Appendix 2 of the study protocol for further details.

No alpha adjustments for multiple comparisons are planned.

For all cohorts, the primary virology analysis will be performed as part of a Day 10 Review (accompanied with key safety review if deemed necessary, see [Section 5.7.1](#)) which is to be completed after all patients enrolled in the current cohort have completed assessments through Day 10. Other endpoints will be analyzed at the completion of each full cohort or at the completion of the study. All analyses at the Day 10 review or at the completion of each cohort will compare each AT-527 dose group and a combined placebo group, including all placebo patients enrolled across cohorts up to the cohort being analyzed, while analyses performed at the completion of the study will compare each AT-527 dose group and a combined placebo group from all cohorts.

Table 3 Differences in Virology Sampling Between Cohorts

Assessment	Cohort A	Cohorts B–E
Nasopharyngeal swab sample for COVID-19 virology	Once a day on Days 1, 3, 5, and 7	Once a day on Days 1, 3, 5, and 7
Saliva sample for COVID-19 virology	NA	Once a day on Days 1, 3, 5, and 7
Serum sample for anti-SARS-CoV-2 antibodies and viral RNA	Once a day on Days 1 and 7	Once a day on Days 1, 3, 5, and 7

COVID-19 = coronavirus disease 2019; NA = not applicable; SARS-CoV-2 = severe acute respiratory syndrome coronavirus-2.

For virology endpoints, the time windows for each assessment are given in [Table 4](#). The time windows will be used for all virology endpoints except the time-to-event endpoints.

Table 4 Virology Assessment Time Windows

Scheduled Timepoint ^{a, b, d}	Acceptable Time Window
Baseline (Day 1 pre-dose)	Day 1 pre-dose ^c
Day 3	Day 2 – Day 3
Day 5	Day 4 – Day 5
Day 7	Day 6 – Day 8

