5.4.2 Secondary Endpoints

5.4.2.1 Secondary Endpoints (Virology)

All secondary virology analyses will be performed on the mITTi population.

All virology analyses will be performed using the nasopharyngeal swab data.

Descriptive analyses of saliva and serum samples will be performed on an exploratory basis for the primary and secondary virology endpoints, as required.

Time to event virology secondary endpoints

For time to event virology secondary endpoints, time will be calculated in hours.

- **Time to cessation of SARS-CoV-2 viral shedding as measured by RT-PCR**
 - Time to cessation of viral shedding by RT-PCR, in hours, is defined as the time between the initiation of any study treatment and first time when a negative or BLQ test result by RT-PCR is obtained. Patients who do not receive a negative or BLQ test result by RT-PCR by the last observation timepoint will be treated as censored at the final timepoint on Day 7.
- **Time to sustained non-detectable SARS-CoV-2 virus RNA**
 - Time to sustained non-detectable SARS-CoV-2 virus RNA, in hours, is defined as the time between the initiation of any study treatment and first time when a negative or BLQ test result by RT-PCR is obtained after which no positive test above or equal to the LOQ was reported. Patients who do not meet this endpoint by the last observation timepoint will be treated as censored at the final timepoint on Day 7.

These time-to-event endpoints will be summarized using descriptive statistics by treatment, as well as Kaplan-Meier plots. The median time to response from the Kaplan-Meier plots will be presented along with the 80% CI. If required, a hazard ratio may be produced adjusting for baseline viral load using a Cox proportional hazards model.

For all cohorts, the virology time-to-event endpoints will be described for the AT-527 group and the pooled placebo group through Day 7 using the mITTi population.

For virology time to event endpoints, deaths will be right censored at Day 7. Consequently, for these endpoints, participants censored on the final day reflect two different states, death or failure to meet the improvement outcome criterion. Therefore, it is important to understand the outcome in the context of the number and timing of deaths by treatment group.

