Intercurrent events are those that occur after treatment initiation and either preclude observation of the variable or affect its interpretation. Intercurrent events and missing data will be accounted for through censoring rules, as described in [Table 7](#) below.

Table 7 Virology Time to Event Censoring

Event	Censor	Date and Time
Death prior to meeting endpoint	Yes	Final timepoint on Day 7
Discontinuation or lost to follow-up up to Day 7 for any reason prior to meeting endpoint	Yes	Last observed virology assessment
Do not meet the endpoint	Yes	Final timepoint on Day 7

Proportion virology secondary endpoint

- **Proportion of patients positive for SARS-CoV-2 virus RNA by RT-PCR at specified timepoints**
 - Proportion of patients positive for SARS-CoV-2 virus RNA by RT-PCR will be presented by treatment at each visit. It is defined as the percentage of patients with a positive virus RNA by RT-PCR test result above or equal to the LOQ.

For virology proportion endpoints in all cohorts, the proportion of patients positive for SARS-CoV-2 virus RNA by RT-PCR will be compared between the AT-527 group and the combined placebo group. For all cohorts, the number, proportion and difference in proportions along with 80% CIs will be presented by treatment group for all timepoints.

Missing data will be treated as missing and will not be included in the analysis. However, if a patient dies, the non-responder rule will apply and the patient will be imputed as positive for all timepoints post-death.

Area under the curve (AUC) virology secondary endpoint

- **Area under the curve in the amount of SARS-CoV-2 virus RNA as measured by RT-PCR**
 - AUC in virus RNA (RT-PCR) will be presented by treatment group and is defined as AUC of the amount of virus RNA (RT-PCR). AUC will be calculated using the trapezoidal method. AUC of change from time 0 (t_0) to time K (t_k) is given by the formula:

$$\sum_{k=1}^K \frac{(y_k + y_{k-1})(t_k - t_{k-1})}{2},$$

where t_k (hours) represents the date of the k^{th} virus RNA (RT-PCR) assessment ($k = 0, \dots, K$) and y_k represents the \log_{10} value of the k^{th} virus RNA (RT-PCR) assessment.

For the virology AUC endpoint, the AUC of the amount of virus RNA (RT-PCR) will be compared between the AT-527 group and a combined placebo group. For all cohorts, summary statistics will be presented to Day 7 using the full combined placebo group.

Missing data will be treated as such and not included in the analysis.

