5.4.2.5 Sensitivity Analyses for Secondary Endpoints

Due to practical constraints, patients may receive first study treatment a day post randomization. Sensitivity analyses may be performed on the following time-to-event virology and efficacy secondary endpoints, defined as the time from randomization to meeting the endpoint:

- Time to cessation of SARS-CoV-2 viral shedding as measured by RT-PCR
- Time to sustained non-detectable SARS-CoV-2 virus RNA
- Time to alleviation or improvement of COVID-19 symptoms (Items 1–12 of the COVID-19 symptom diary)
- Time to alleviation of COVID-19 signs and symptoms

Sensitivity analyses may also be performed for the following time-to-event virology secondary endpoints where results reported as BLQ are treated as positive (instead of negative):

- Time to cessation of SARS-CoV-2 viral shedding as measured by RT-PCR
- Time to sustained non-detectable SARS-CoV-2 virus RNA

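### Sustained non-detectable RNA can rest on one unconfirmed last swab, and the SAP leaves out the Cohort E Day 14 swab that could test it

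*SAP*

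**What the plan says.** Protocol 6.4.2.1 lists the endpoint without defining it, so the SAP wording governs.

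- **Event.** SAP 5.4.2.1 requires that a "negative or BLQ test result by RT-PCR is obtained after which no positive test above or equal to the LOQ was reported". It asks for no later swab, no confirming negative and no minimum duration.
- **Companion endpoint.** Cessation of viral shedding uses the "first time when a negative or BLQ test result by RT-PCR is obtained", whatever follows.
- **Follow-up.** One limit serves every cohort: "the virology time-to-event endpoints will be described for the AT-527 group and the pooled placebo group through Day 7 using the mITTi population".
- **Sampling.** SAP Table 3 gives the nasopharyngeal swabs as "Once a day on Days 1, 3, 5, and 7". Protocol Appendix 2 agrees for Cohorts B–D: "Nasopharyngeal swab samples should be collected at screening and once per day on Days 1, 3, 5, and 7". Appendix 1 has the same days for Cohort A.
- **Censoring.** Table 7 censors at the last virology assessment for "Discontinuation or lost to follow-up up to Day 7 for any reason prior to meeting endpoint". Someone who has already met the definition is not censored.
- **Cohort E.** Protocol version 6 adds a Day 14 swab. Appendix 3, footnote d, states: "Patients in Cohort E are required to have an in-person visit for nasopharyngeal swab collection". Protocol 6.4.1 analyses the Cohort E primary endpoint at Days 3, 5, 7 and 14.
- **Sensitivity analyses.** SAP 5.4.2.5 allows a change of time origin or of BLQ handling for this endpoint. Neither concerns confirmation.

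**The concern.** An endpoint labelled sustained should separate lasting clearance from a chance low reading or a rebound. This definition asks only that no later positive was reported, and a patient with no later swab cannot fail that test. Absence of follow-up is then read as evidence of durability.

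The symptom endpoints in the same SAP must hold for 21.5 or 43 hours; this virology endpoint has no comparable requirement. Since BLQ also counts, a single swab below 120 copies/mL is enough. Kaplan-Meier medians with 80% CIs are planned, and log-rank or Cox analyses are possible. A result could therefore be reported as sustained clearance although part of it was never tested for durability.

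**Working it through.** The plan states no figure for this endpoint, so there is none to reproduce. The check applies the SAP rule to every possible swab sequence.

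**1. Complete data, Days 3/5/7.** Here + means at or above LOQ and − means negative or BLQ.

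| Pattern | Cessation event | Sustained event | Swabs after sustained event |
|---|---|---|---|
| + + + | none | none | n/a |
| + + − | Day 7 | Day 7 | 0 |
| + − + | Day 5 | none | n/a |
| + − − | Day 5 | Day 5 | 1 |
| − + + | Day 3 | none | n/a |
| − + − | Day 3 | Day 7 | 0 |
| − − + | Day 3 | none | n/a |
| − − − | Day 3 | Day 3 | 2 |

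Four of the eight patterns are credited, and they are exactly the four with a negative or BLQ Day 7 swab. With complete data the number of sustained events is therefore the complement of the proportion positive at Day 7, which is already a secondary endpoint. Only the timing is new. Two of the four credited patterns have no later swab. For `+ + −`, event and time equal those for cessation.

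**2. Missing swabs (shown as a dot).** `− . .`, `+ − .` and `. − .` are also credited with no later swab.

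**3. Early termination.** Protocol 4.6.2 sets this visit 7 (±2) days after the final dose, and the schedules mark a nasopharyngeal swab there. For a final dose on Day 3, the visit falls on Day 3 + 7 ± 2, that is Days 8 to 12, beyond the Day 7 limit. The no-later-positive clause has no time limit of its own, and SAP 5.1 exempts time-to-event endpoints from the visit windows. Read literally, a positive swab at that visit defeats the event. The SAP does not say so, and a patient who never attends stays credited.

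**4. Adding Day 14 in Cohort E.** Four swabs give 16 patterns, of which the 8 with a negative Day 14 swab are credited. In 4 of these the Day 7 swab is also negative, so the event is dated Day 7 or earlier with at least one later negative. In the other 4 the Day 7 swab is positive, so the event is dated Day 14 with nothing after it. `+ + − −` becomes a confirmed Day 7 event, and `+ + − +` is no longer credited.

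**5. Size, by assumption only.** Let *a* and *b* be the cumulative proportions with a sustained event by Day 5 and Day 7. The share resting on the Day 7 swab alone is (*b* − *a*)/*b*.

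- 5% and 15%: 10/15 = 67%
- 10% and 25%: 15/25 = 60%
- 20% and 40%: 20/40 = 50%
- 30% and 40%: 10/40 = 25%

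These inputs are invented, and the spread shows that the share cannot be fixed from the documents.

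**6. What confirmation would buy, by assumption.** Suppose a patient truly positive throughout reads below LOQ on any swab with independent probability *q*. With complete data the present rule credits that patient with probability *q*; requiring Days 5 and 7 both negative gives *q*². For *q* = 5%, 10% and 20%, the probability falls to 0.25%, 1% and 4%.

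**The case against.** The best defence is that the endpoint is secondary and descriptive in a study the plan calls hypothesis-generating. The Kaplan-Meier steps show how many events fall near Day 7, and proportion positive is reported at every visit. That stands, and it keeps the point modest.

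Four stronger readings are tempting, and the documents do not support them.

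- **Every dropout after a negative is credited untested.** A reader might infer this from Table 7, but patients leaving the study are due an early-termination swab. The gap is confined to those who do not provide it.
- **The SAP chose to ignore Day 14 in Cohort E.** SAP 1.2 still describes Cohort E as 40 patients randomised 3:1, with a Day 14 telephone call. Protocol version 6 has about 224 patients at 1:1 and an in-person visit. The omission follows from that mismatch rather than from a decision about this endpoint. It is also unclear whether a Day 14 positive would count, since the no-later-positive clause is open-ended.
- **The affected share can be read from first negatives on Day 7.** First negatives define cessation. `− + −` is a sustained Day 7 event without being a first negative on Day 7, and `− + +` has a first negative but is never sustained.
- **Confirmation should replace the main definition everywhere.** In Cohorts A–D that would censor `+ + −` at Day 7 exactly like `+ + +`, hiding any effect that brings clearance to Day 7. It would also show little about durability after treatment: the tenth dose falls on Day 5 evening or Day 6 morning, so Day 7 is only one to two days later. That limit comes from the sampling, not the wording.

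None of this answers the core point: no passage requires a confirming negative.

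**Conclusion.** The concern holds in a limited form. On the SAP's wording, a negative or BLQ result on the last available swab counts as sustained without confirmation. That follows from the definition and needs no assumption. Events dated Day 3 or Day 5 with later swabs are tested for durability; Day 7 events, and events in patients lost without an early-termination swab, are not. How many events this affects is unknown, because it depends on clearance and dropout rates the documents do not give.

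The consequence is a label stronger than the evidence behind it on one descriptive secondary endpoint. The primary analysis and sample size are unaffected. In Cohort E the means of testing Day 7 negatives is already scheduled, so using it is a cheap improvement.

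**What to change.** 1. **Cohort E.** In SAP 5.4.2.1 and Table 7, run this endpoint and its censoring through Day 14, so that the Day 14 swab confirms or refutes a Day 7 negative. State that any later result at or above LOQ, including at Day 14 or early termination, defeats the event. Make this change when the SAP is aligned with protocol version 6; protocol Section 6 has the SAP finalised before the end of the study. Footnote o of protocol Appendix 3 still lists swabs only to Day 7 and should be reconciled with the schedule grid and footnote d.
2. **Cohorts A–D.** Keep the main definition. Add to SAP 5.4.2.5 a sensitivity analysis requiring at least one later negative or BLQ swab, with no later result at or above LOQ. Report by arm the number of events whose qualifying negative is the last available swab; this wording also covers `− + −`.

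The cost is SAP text and a little more programming, with no new visits or samples. The sensitivity analysis will have fewer events: in Cohorts A–D, on scheduled swabs, only negatives first obtained on Day 3 or Day 5 can be confirmed, so its median may not be reached. Negatives first obtained on Day 14 in Cohort E remain unconfirmed.

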These endpoints will be summarized using descriptive statistics by treatment group, as well as Kaplan-Meier plots where appropriate. The median time to response will be presented along with the 80% CI. For all cohorts, the efficacy time to event endpoints will be described through Day 28 between the AT-527 group and the combined placebo group from all available cohorts using the mITTi population.

A summary of the symptom severity for each symptom in the COVID-19 symptom diary will be provided at baseline, Day 14 and Day 28 for each treatment group and pooled placebo group. Day 14 (morning) assessments are to be used for the Day 14 summary. If the morning sample is missing, the evening sample will be used.

For efficacy time to event endpoints, deaths will be right censored at Day 28. Consequently, for these endpoints, participants censored on Day 28 reflect two different states, death and failure to meet the improvement outcome criterion. Therefore, it is

important to understand the outcome in the context of the number and timing of deaths by treatment group.

Intercurrent events are those that occur after treatment initiation and either preclude observation of the variable or affect its interpretation. Intercurrent events and missing data will be accounted for through censoring rules, as described in [Table 9](#) below.

Table 9 Efficacy Time to Event Censoring

Event	Censor	Date and Time
Death prior to meeting endpoint	Yes	Final timepoint on Day 28
Discontinuation or lost to follow-up up to Day 28 for any reason prior to meeting endpoint	Yes	Last observed COVID-19 symptom diary assessment
Do not meet the endpoint	Yes	Final timepoint on Day 28

Frequency efficacy endpoints include:

- **Frequency of COVID-19-related complications**
 - COVID-19-related complications include: death, hospitalization, radiologically confirmed pneumonia, acute respiratory failure, sepsis, coagulopathy, pericarditis, myocarditis, and cardiac failure.

For frequency efficacy endpoints, the number, proportion and difference in proportions between the AT-527 group and the pooled placebo group from all available cohorts, along with 80% CIs will be presented by treatment group.

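### Patients who stay in the study but whose swabs or diaries stop early are censored at Day 7 or Day 28, so unobserved time counts as event-free time at risk (minor)

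*SAP*

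**What the plan says.** SAP 5.4.2.1 defines two virology time-to-event endpoints: time to cessation of shedding and time to sustained non-detectable RNA. For the second it says: "Patients who do not meet this endpoint by the last observation timepoint will be treated as censored at the final timepoint on Day 7". The sentence for the first ends the same way: "by the last observation timepoint will be treated as censored at the final timepoint on Day 7". Neither sentence makes an exception for patients whose swabs ended sooner.

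The section then states: "Intercurrent events and missing data will be accounted for through censoring rules", and points to Table 7. Table 7 has three rows:
- Death before the endpoint: censored at the final Day 7 timepoint.
- "Discontinuation or lost to follow-up up to Day 7 for any reason prior to meeting endpoint": censored at "Last observed virology assessment".
- Endpoint not met: censored at the final Day 7 timepoint.

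Table 9 (SAP 5.4.2.3) has the same structure for the symptom endpoints. Its second row, "Discontinuation or lost to follow-up up to Day 28 for any reason prior to meeting endpoint", is censored at "Last observed COVID-19 symptom diary assessment". The other two rows use the final Day 28 timepoint.

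The SAP's amendment rationale explains the Day 7 rule as a way to keep patients at risk so that the Kaplan-Meier plots can be read at Day 7. The Day 28 rule was aligned with it.

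**The concern.** The three rows do not cover everyone. A patient who has not died, withdrawn or been lost, but has no final swab or has stopped the diary, can only be placed in the third row. The patient then stays in the risk set until Day 7 or Day 28 although no event could have been recorded after the last assessment.

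Such patients are plausible. The diary is on paper and self-completed, twice daily to Day 14 and once daily to Day 28 (Protocol 4.5.7.2). In Cohorts A–D the only scheduled contacts after Day 7 are telephone calls on Days 14 and 33 (Protocol Appendices 1 and 2). A patient can therefore let the diary lapse and still complete the study.

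The gap sits badly with the rest of the SAP. Table 7 is presented as handling missing data, yet no row covers missing data without discontinuation. The SAP tells readers that patients censored on the last day are either deaths or failures to meet the criterion. A third group, not observed to that day, goes unmentioned. For the primary, proportion and AUC endpoints, missing values are generally left out (the proportion endpoint counts patients as positive after death).

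At stake are the Kaplan-Meier curves, the medians with their 80% CIs, and any optional log-rank test or hazard ratio.

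**Working it through.** The plan gives no event rate, power or lapse rate for these endpoints, so there is no figure of its own to reproduce. All rates below are assumptions. Lapse is taken as unrelated to outcome.

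**1. Small worked example, swabs on Days 3, 5 and 7.** Take 27 patients (the per-group planning figure in SAP section 3). Three clear at Day 3. Three more then give no further swabs but stay in the study. Four clear at Day 5 and five at Day 7.
- Censored at Day 7: S = (24/27)(20/24)(15/20) = 15/27, so the response is 44.4%, which is simply 12/27.
- Censored at last swab: S = (24/27)(17/21)(12/17) = 0.508, so the response is 49.2%.
- Had those three formally discontinued or been lost, Table 7 would already give 49.2%.

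**2. Expected Day 7 response.** Let the conditional clearance be h3, h5, h7, with a share m stopping swabs after Day 3. If everyone without the event is held to Day 7, the estimate is the share with a recorded event:

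reported = true − m(1 − h3)[1 − (1 − h5)(1 − h7)]

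| h3 / h5 / h7 | True | m = 5% | m = 10% | m = 20% |
|---|---|---|---|---|
| 5 / 10 / 20% | 31.6% | 30.3% | 28.9% | 26.3% |
| 10 / 20 / 30% | 49.6% | 47.6% | 45.6% | 41.7% |
| 20 / 30 / 50% | 72.0% | 69.4% | 66.8% | 61.6% |

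For the middle row, true = 1 − 0.9 × 0.8 × 0.7 = 0.496 and the loss is 0.9 × 0.44 × m = 0.396m. Censoring at the last swab returns the true value in every cell. With no drug effect and lapse of 5% in one arm and 15% in the other, the arms differ by 0.10 × 0.266, 0.10 × 0.396 or 0.10 × 0.52, that is 2.7, 4.0 or 5.2 points.

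**3. Expected Day 28 alleviation.** Take exponential times with median 12 days, so λ = ln 2 / 12 = 0.0578 and F(28) = 1 − 2^(−28/12) = 80.2%. A share p stops the diary at a time C uniform on Days 3 to 21. The chance of the event before stopping is

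E[F(C)] = 1 − (e^(−3λ) − e^(−21λ)) / (18λ) = 1 − (0.841 − 0.297)/1.040 = 0.477.

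Reported at Day 28 = (1 − p)(0.802) + p(0.477):
- p = 10%: 76.9%
- p = 20%: 73.7%
- p = 30%: 70.4%

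The reported median solves (1 − p)F(t) + p·E[F(min(C, t))] = 0.5. It moves from 12.0 days to 12.3, 12.6 and 13.0 days. Censoring at the last diary entry keeps 80.2% and 12.0 days.

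**4. Optional log-rank test, same model, no drug effect, two-sided 20%, by simulation.**
- 27 per arm, lapse 10% v 30%: rejects about 23% to 24% of the time, against about 20% with last-diary censoring.
- Equal 10% lapse in both arms: no inflation.

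**The case against.** Three stronger readings are tempting, and the documents do not support them.

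*Everyone whose data stop early is moved to Day 7 or Day 28.* A reader of the two sentences in SAP 5.4.2.1 alone might infer this. Tables 7 and 9 already censor discontinued and lost patients at their last observed assessment, and for them there is no bias if stopping is unrelated to outcome. Table 7 is the controlling detail, so the mismatch with the sentences needs only a cross-reference.

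*Unobserved time is scored as failure.* It is not. These patients are censored. The distortion comes from leaving them in the risk set.

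*The error rate of the tests is seriously inflated.* With 100 per arm and lapse of 10% v 30%, the simulated null rejection is about 31% to 34%. But 100 per arm is the protocol's Cohort E figure, which this SAP does not describe (it has 40 patients in each of Cohorts B–E). The result also needs a threefold lapse imbalance in a double-blind trial, for tests the SAP makes optional.

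It is also fair to say that the final-day rule is deliberate, that it is right for patients assessed to that day, and that its use for deaths is stated openly: "For virology time to event endpoints, deaths will be right censored at Day 7". Since discontinuation and loss to follow-up are not defined, some lapsed patients might be placed in the second row in practice. For swabs, missing only the Day 7 sample adds about two unobserved days.

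What stands is the missing row. Making a plot easier to read does not justify crediting time in which nothing was observed.

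**Conclusion.** The gap is real and narrow. It affects only patients who remain in the study, have not met the endpoint, and lack assessments to the final day. For them the rule lowers the response curve and delays the median, even when lapse is equal between arms. The loss is about 3 to 10 points at Day 28 for 10% to 30% diary lapse, and about 2 to 8 points at Day 7 for 5% to 20% swab lapse in the middle scenario. The shift in the median is under one to about one day. Distortion of a comparison needs unequal lapse and is small at the SAP's planning size.

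These sizes rest on assumed lapse rates, an exponential model for symptoms, and lapse unrelated to outcome. If patients stop the diary because they have recovered or become sicker, censoring at the last entry is not free of bias either, which is why counts by arm matter. Severity is minor: the endpoints are secondary and descriptive with 80% CIs, and the primary ANCOVA does not use these rules.

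**What to change.** In the SAP:
- Add a row to Tables 7 and 9 for patients still in the study, without the event and without a final assessment. Censor them at the last evaluable swab or diary entry.
- Keep the final Day 7 or Day 28 time for patients assessed to that day and for deaths.
- Make the two non-responder sentences in 5.4.2.1 refer to Table 7.
- State that discontinuation in both tables means leaving the study. Table 4, footnote b, says that patients who only stop study drug continue to be assessed.
- Report, by arm, the number censored before the final day and when.

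The cost is a few lines of SAP text and one derivation rule. No new data are needed.
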